1.2 Specific Aims/Objectives

#1 (Feasibility; Primary Aim): To determine the feasibility and acceptability of the PATH intervention in patients with hematologic malignancy undergoing HSCT.

PROTOCOL TITLE: Randomized Trial of a Positive Psychology Intervention for Patients with Hematologic Malignancies Undergoing Hematopoietic Stem Cell Transplantation

Hypothesis: The PATH intervention will be deemed feasible with >75% of participants randomized to the intervention arm completing ≥ 6/9 positive psychology exercises. The PATH intervention will be deemed acceptable with mean ease and utility scores of each exercise being ≥ 7/10.

#2 (Effects on Patient-Reported Outcomes): To assess the preliminary efficacy of the PATH intervention on psychological (e.g., depression, anxiety, optimism, positive affect), QOL, and functional outcomes compared to the usual care condition.

Hypothesis: Patients randomized to the PATH intervention will have improved PPWB (e.g., optimism, positive affect, gratitude), mood (e.g., depression and anxiety), and QOL compared to those in the usual care condition.

#3 (Effects on Health Behaviors): To examine the impact of the PATH intervention on behavioral outcomes (e.g., medication adherence, physical activity) compared to those in the usual care condition.

Hypothesis: Patients randomized to the PATH intervention will have improved behavioral outcomes (e.g., medication adherence, physical activity) compared to those in the usual care condition.

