9.2 The PATH Intervention

Participants randomized to the PATH intervention will meet (via phone) with the interventionist around approximately day 100 post-HSCT. After the initial phone visit to introduce positive psychology and the PATH intervention, participants will be asked to complete 9 weekly positive psychology exercises. The interventionist will then meet weekly with patients via phone to review each positive psychology exercise.

PROTOCOL TITLE: Randomized Trial of a Positive Psychology Intervention for Patients with Hematologic Malignancies Undergoing Hematopoietic Stem Cell Transplantation

Table 2. PP intervention component: modules and exercises. Intervention content will be customized to HSCT context.

Module 1: Gratitude/positive affect-based exercises		
Week 1	Gratitude for positive events ⁷	Participants identify three positive events that have occurred in the past week and reflect on their feelings as they recall and describe these events.
2	Gratitude letter ⁷	Participants write a letter of gratitude thanking a person for their support or kindness.
3	Gratitude skills application	Participants select a useful activity from the prior two weeks, consider how to adapt the activity to daily life, and develop a plan to utilize this skill regularly.
Module 2: Strengths-based exercises		
Week 4	Recalling past success ⁵⁸	Participants recall an event in which they experienced success, then write about the event, their contribution to the success, and positive feelings elicited by recalling it.
5	Using personal strengths ⁷	Participants undergo a brief assessment of personal strengths, then find a specific new way to use one of their 'signature strengths' in the next 7 days.
6	Strength-based skills application	Participants select a useful activity from the prior two weeks, consider how to adapt the activity to daily life, and develop a plan to utilize this skill regularly.
Module 3: Optimism and meaning-based exercises		
Week 7	Enjoyable and meaningful activities ⁵⁹	Participants complete three activities: an enjoyable activity alone, an enjoyable activity with another person, and a meaningful activity completed alone or with others.
8	The good life ⁶⁰	Participants imagine and write in detail about a best possible (realistic) future one year from now and consider small short-term steps to take toward such a future.

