Weekly phone sessions for positive psychology intervention: Participants in the intervention group will be asked to complete the 9 weekly PP exercises and to speak with the interventionist weekly. Weekly phone sessions will last approximately 15-20 minutes. Prior to completing each phone session, participants will be asked to rate their current level of happiness and optimism, using a 10-point Likert scale. Immediately after completing the exercise and phone session, participants will rate the ease of exercise/session completion, overall utility of the exercise/phone session, and their current levels of happiness and optimism, all using 10-point Likert scales. These calls will be recorded using the SONY IC Recorder ICD-PX370 so that a percentage (10%) of these recordings can be reviewed by [name], to ensure that the PP intervention is being delivered as described in the protocol. Given the results of our prior PP studies in medical populations yielding a 64-85% completion rate of the exercises, our recent proof-of-concept trial (18-225) yielding 100% completion rate in this population, and given that this is a feasibility study (i.e., we want to assess participants' willingness to complete the phone sessions), we will expect participants to complete at least 6 PP exercises. In other words, if a participant completes at least 6 sessions, missed sessions will not be considered a deviation from the protocol.

All participants will receive a \$50 check after completion of the intervention. Participants in the usual care group will also receive a \$50 at the same timepoint. All participants (in either the usual care group or intervention group) who complete 18-week follow-up assessments will receive an additional \$50 check.

PROTOCOL TITLE: Randomized Trial of a Positive Psychology Intervention for Patients with Hematologic Malignancies Undergoing Hematopoietic Stem Cell Transplantation

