10.0 Data and Specimen Banking: Not Applicable

10.1. *Data analysis*

Specific Aim 1 (Feasibility; Primary Aim): To demonstrate the feasibility of the PATH intervention in patients with hematologic malignancy undergoing HSCT: Based on prior work, we define feasibility as >75% of enrolled participants who start the intervention completing at least 6 of the

PROTOCOL TITLE: Randomized Trial of a Positive Psychology Intervention for Patients with Hematologic Malignancies Undergoing Hematopoietic Stem Cell Transplantation

9 PP sessions, consistent with metrics used in prior positive psychology feasibility trials^{17, 54} and other behavioral intervention studies.⁸⁵⁻⁸⁷ We will estimate the feasibility using the proportion who meet the criteria, and we will place an exact 95% binomial confidence interval around the proportion. We will assess acceptability using weekly ratings of ease and utility of each exercise (0=very difficult/not helpful; 10=very easy/very helpful). The mean ease and utility of each exercise and overall will be calculated, and will use a threshold of a mean combined score of 7.0/10 for acceptability that was used in prior studies.^{19,57}

Specific Aim 2 (Effects on Patient-Reported Outcomes): To assess the preliminary efficacy of the PATH intervention on psychological (e.g., depression, anxiety, optimism, positive affect), QOL, and functional outcomes compared to the usual care condition: Analyses will begin with descriptive and graphical summaries of the endpoints and evaluation of whether a normality assumption is reasonable for the endpoint or whether transformation is necessary. We will use a Bonferroni correction to address multiple measures and testing. All statistical tests will be two-sided with a liberal alpha level of 0.2 to detect a signal on the impact of the intervention on patient- reported outcomes. We will summarize participants' baseline characteristics using descriptive statistics (e.g., mean) for continuous variables and proportions for categorical variables.

To examine the immediate impact of the intervention on happiness and optimism, we will use generalized estimating equations (GEE) to determine the immediate impact of a PP session on optimism and happiness. The GEE model will allow us to account for the repeated observations on subjects from the different exercises.

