Based on prior trials in this population,⁹² we anticipate 15% of enrolled participants will be unable to complete the intervention due to medical complications and mortality. Hence, we will enroll 70 participants (35 in the [PATH] PP arm) to target having at least 30 PP participants who complete the intervention. For our primary aim (feasibility), in prior trials, approximately 80% of participants have completed 6 of 9 PP exercises.⁹ Using the same rate, with 30 PATH participants, we will have 95% power (two-sided $\alpha = .05$, binomial proportion test) to demonstrate that the proportion who complete > 6 of 9 PP sessions is larger than 50% (i.e., a majority). For acceptability, using this sample size, we will have 95% power to detect a true mean score of > 7.0 based on prior work (in which mean utility scores were 7.8 ± 1.8).¹² This pilot RCT is not designed to definitively detect significant ($p < .05$) group differences in psychological, QOL, or behavioral outcomes (and we would need between-group effect size differences of $d = .74$ to be powered at 80% to detect significant differences). However, this sample of 30 completers in each group will allow us to preliminarily explore the impact of PATH on clinical outcomes and make tentative estimations of effect sizes.

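### The primary >75% feasibility rule counts exercises among all randomized to PATH in section 1.2 but sessions among starters in section 10.1, and completion is defined for neither

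*Combined protocol and SAP*

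**What the plan says.** - Section 1.2, Aim 1, sets the hypothesis as ">75% of participants randomized to the intervention arm completing ≥ 6/9 positive psychology exercises". The unit is the exercise and the denominator is everyone randomized to PATH.
- Section 10.1, Specific Aim 1, says "we define feasibility as >75% of enrolled participants who start the intervention completing at least 6 of the" and continues, after the page break, "9 PP sessions, consistent with metrics used in prior positive psychology feasibility trials". The unit is now the session and the denominator is those who start.
- Section 9.7 states an expectation of at least 6 exercises and then rephrases it in the other unit: "if a participant completes at least 6 sessions, missed sessions will not be considered a deviation from the protocol".
- Section 10.2 takes an 80% rate for 6 of 9 exercises from prior trials. It then gives 95% power, with 30 PATH participants, "to demonstrate that the proportion who complete > 6 of 9 PP sessions is larger than 50" per cent.
- Section 9.2 places an introductory call before the nine exercises: "After the initial phone visit to introduce positive psychology and the PATH intervention".

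No section says what record makes an exercise or a session completed, or what event counts as starting the intervention.

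**The concern.** This is the primary endpoint, and it carries a fixed pass mark. An exercise and a session are related but separate events. Sections 9.1 and 9.2 have the participant do the exercise during the week and then review it by phone. Section 9.7 says each call also explains and assigns the next exercise, so a call can take place when that week's exercise was not done, and an exercise can be done when the call is missed. Table 3 in section 9.2 plans to measure the number of intervention visits, so a visit count will exist beside any exercise count.

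The denominators can also differ. Section 5.1 places randomization after the baseline assessments, and section 9.2 places the first intervention call at about day 100. A patient can therefore be randomized to PATH and never start.

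If the unit and the denominator are settled only once the data are in, the same data could be reported as feasible or not feasible.

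**Working it through.** **The statements side by side**

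| Section | Unit | Cut-off | Denominator | Benchmark |
|---|---|---|---|---|
| 1.2 | exercises | at least 6 of 9 | randomized to PATH | >75% |
| 10.1 | sessions | at least 6 of 9 | those who start | >75% |
| 9.7 | both, as equivalents | at least 6 | none (deviation rule) | none |
| 10.2 | exercises for the 80% input, sessions for the powered event | 6 of 9 for the input, more than 6 of 9 for the event | 30 PATH participants | 50% |

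**1. The plan's own figure.** Inputs from section 10.2: n = 30, p0 = 0.50, p1 = 0.80, two-sided α = 0.05.
- Exact: the smallest r with P(X ≥ r | 30, 0.50) ≤ 0.025 is 21 (tail 0.0214; r = 20 gives 0.0494). Power = P(X ≥ 21 | 30, 0.80) = 93.9%.
- Normal approximation: Φ[(0.30 − 1.96·√(0.25/30)) / √(0.16/30)] = Φ[(0.30 − 0.179)/0.0730] = Φ(1.66) = 95.1%.

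The stated 95% is reproduced, using the rate that the plan gives for 6 of 9. For at least 7 of 9 the plan gives no rate, and the true rate cannot be higher than the rate for at least 6. If it were lower, exact power against 50% at n = 30 would be as follows (assumed rates): 0.75 gives 80.3%, 0.70 gives 58.9%, 0.65 gives 35.8% and 0.60 gives 17.6%.

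**2. The pass mark.** 0.75 × 35 = 26.25, so more than 75% of 35 means 27 (27/35 = 77.1%). 26/35 = 74.3% fails.

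**3. Effect of the unit, denominator fixed at 35.** Suppose 28 complete at least 6 exercises: 28/35 = 80.0%, a pass. If two of these took part in fewer than 6 calls, and nobody differs in the other direction, the session count is 26/35 = 74.3%, a fail.

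**4. Effect of the denominator, unit fixed.** With 26 completers, 26/35 = 74.3% fails. If one randomized patient never started, 26/34 = 76.5% passes.

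The plan's own assumptions lead close to the mark. Section 10.2 expects about 30 of 35 to be able to complete, and an 80% rate: 0.80 × 30 = 24. Then 24/35 = 68.6% fails. Among starters the answer depends on how many of the other five began: 24/30 = 80.0% and 24/31 = 77.4% pass, while 24/32 = 75.0% does not exceed 75%. The plan does not say how many of the five would start, so 30 starters is the extreme case.

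**The case against.** The strongest reply is that the authors plainly regard exercise and session as one thing. Section 9.7 joins them as restatements of each other and has participants rate them as a single item, section 9.1 describes both a nine-session intervention and nine weekly exercises, and every call reviews that week's exercise. This stands as evidence of intent: the text does not set up two rival endpoints. It does not supply a definition, and it says nothing about randomized versus started.

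A second reply is that completion may be too high for any of this to matter, since section 9.7 cites 100% in the proof-of-concept trial. That is possible. But the same section cites 64–85% in other medical populations, and section 10.2 plans on 80% after 15% attrition.

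Three stronger readings are tempting and not supported.
- A reader might infer that the strict inequality in section 10.2 moves results across the 75% mark. It does not: both statements of the 75% rule use at least 6, and the strict form appears only in the power sentence, where the benchmark is 50%.
- A reader might size the problem with a binomial model: nine independent weeks at 0.80 each give 91% reaching at least 6 and 74% reaching at least 7. That compares cut-offs the 75% rule never uses. It also contradicts the plan's 80% for 6 of 9 and assumes independent weeks, although the complications and deaths that section 10.2 expects would cluster missed weeks.
- A reader might count the introductory call as a session. The total is nine throughout, and section 9.7 assigns the first exercise in preparation for the first phone session, so this reading is weak.

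**Conclusion.** The concern holds in a limited form. The primary >75% rule has two units and two denominators, and no definition of completion. With 35 in the PATH arm, one patient who never starts, or two patients whose exercise and call counts differ, is enough to reverse the conclusion when the result lies near the mark. The counts in steps 3 and 4 are illustrations, since the documents give no figure for how often the two units disagree or how many randomized patients will not start. I read the 75% rule as applying to the observed proportion; section 10.1 adds an exact 95% interval but gives it no role in the decision.

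The threshold in section 10.2 is a separate wording error, most plausibly a slip for at least 6. It affects neither the 75% decision nor the sample size. The sentence in section 9.7 governs protocol deviations and should not be read as a third endpoint definition.

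**What to change.** State the rule once and use it in sections 1.2, 9.7, 10.1 and 10.2:
- **Unit.** Choose exercises or sessions. Exercises need the fewest edits, being the unit of Aim 1 and of the 80% input. Requiring both the exercise and its call would be a new criterion, stricter than either existing statement, and is not needed.
- **Completion.** Say what record shows that one unit was completed. For clarity, note that the introductory call is not one of the nine.
- **Denominator.** Use all participants randomized to PATH, as in section 1.2 and in line with the intention-to-treat principle in section 10.1. Those who never start, withdraw or die before reaching six then count as non-completers.
- **Cut-off.** Change > 6 to ≥ 6 in section 10.2.
- **Supportive results.** Report the other unit's count and the starters-only proportion, with a definition of starting.

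The cost is wording only, and the sample size does not change. The one drawback is that the headline proportion may be slightly less favourable, since it cannot exceed the proportion among starters.

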8.0 Study Endpoints*

Primary Endpoint:

- Establish feasibility and acceptability of the PATH intervention in the intervention group.

Secondary Endpoints:

- Compare patients' QOL (FACT-BMT) scores longitudinally between the study groups
- Compare patients' positive psychological wellbeing factors [e.g., optimism (LOT-R) and positive affect (PANAS)] between the study groups
- Compare patients' symptoms of anxiety and depression (HADS) between the study groups
- Compare patients' post-traumatic stress symptoms (PCL-C) between the study groups
- Compare patients' fatigue (PROMIS-fatigue) scores between the study groups
- Compare patients' physical activity (Actigraph GT3X+ data) and physical functioning (PROMIS-PF-20) between the study groups
- Compare patients' medication adherence (MEMS Cap data, SSEQ, MARS-5) between the study groups
- There are currently no anticipated primary or secondary safety endpoints.

Exploratory Endpoints:

- Compare patients' coping (Brief Cope) between the study groups
- Assess whether group differences in patient reported QOL are mediated by improved mood (mediator: HADS) or coping (mediator: Brief Cope)

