Participants randomized to the intervention group will be asked to complete 9 weekly PP exercises and to speak with the study interventionist, weekly. Immediately after the completion of each exercise, participants will rate the ease of exercise completion, overall utility of the exercise, and their current levels of positive affect. Prior to the last week of the intervention, all participants (regardless of whether they are in the intervention group or usual care group) will be mailed (or given in person at a routine follow-up clinic visit) an accelerometer to be worn for 7 days prior to the follow-up survey. After the Week 9 intervention phone session, all participants (regardless of whether they are in the intervention group or usual care group) will repeat self-assessment questionnaires completed at baseline either over the phone, in-person at a routine clinic visit or via a REDCap survey link emailed to participants. Additionally, participants randomized to the intervention group will be asked to complete a recorded exit interview (Appendix F) over the phone. At study completion, we will inquire about participants' potential interest in being contacted about our future studies. We will adhere to any and all participant requests regarding contact. Participants will also return the accelerometer and MEMS Caps at the end of the study via mail or in person during a routine follow-up clinic visit. All participants will receive a \$50 check after the 9-week follow-up assessments. Participants who complete the 18-week follow-up assessments will receive an additional \$50 check.

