Follow-up assessments: During Week 8 of the intervention, all participants (those in the intervention group and the usual care group) will be mailed (or given in-person during a routine follow-up clinic visit) an accelerometer to wear for 7 days in order to assess physical activity at follow-up. Then, at Week 9, participants will return the accelerometer and MEMS Cap, and will repeat self-assessment questionnaires obtained at the beginning of the study either in-person during a routine follow-up clinic visit, over the phone, or via a REDCap survey link e-mailed to them, depending on participant's preference. Furthermore, participants in the intervention group will be asked to provide feedback about the program via a recorded exit interview over the phone.

Positive Psychology Program Content: All phone sessions will include (a) a review of the ease and utility of the week's PP exercise, (b) a discussion of the rationale of the next week's PP exercise through a guided review of the PP manual, and (c) assignment of the next week's PP exercise. During the calls, the interventionist and participant will also review the next section of the treatment manual and prepare for the upcoming week's exercise.

9.8 *Procedures performed to lesson the probability or magnitude of risks*

We will ensure that contact with participants is confidential by using only the phone numbers and other contact information that are specifically allowed by the participants. We will not leave study-related messages for participants unless expressly allowed by participants. Upon enrollment, we will ask all participants for the preferred times for calls and if it is acceptable to leave voice messages on their phones. We will adhere to any and all patient requests regarding contact.

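### The weekly ease and utility ratings behind the acceptability endpoint are given two different times and two different objects, and the plan does not say who records them

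*Combined protocol and SAP*

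**What the plan says.** Section 8.0 gives the primary endpoint as "Establish feasibility and acceptability of the PATH intervention in the intervention group". Section 1.2 sets the acceptability criterion on the mean ease and utility scores of each exercise, at 7/10 or above. Section 10.1 agrees on what is rated, "We will assess acceptability using weekly ratings of ease and utility of each exercise", and applies a 7.0/10 threshold to a combined mean.

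The rating itself is described twice.

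- Section 9.1: "Immediately after the completion of each exercise, participants will rate the ease of exercise completion, overall utility of the exercise".
- Section 9.7, on the weekly phone sessions: "Immediately after completing the exercise and phone session, participants will rate the ease of exercise/session completion, overall utility of the exercise/phone session".

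On the content of the calls, section 9.2 says "The interventionist will then meet weekly with patients via phone to review each positive psychology exercise". The program-content paragraph of 9.7 says "All phone sessions will include (a) a review of the ease and utility of the" week's exercise.

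Section 9.6 names REDCap for patient-reported data in general. Its Table 4 has columns only for baseline, Week 9 and Week 18, and the weekly ratings do not appear there. No section states who collects them, by what route, or whether the interventionist sees them.

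**The concern.** The acceptability verdict comes from one arm and a fixed cut. No control group would subtract anything extra that the rating picks up, so what is rated, and when, feeds straight into the verdict.

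Staff who follow 9.1 and staff who follow 9.7 would collect different scores under the same name. The 9.7 score includes the patient's view of the phone session, while the rule in 1.2 and 10.1 is about the exercise. It is also given just after the patient has talked through ease and utility with the person delivering PATH. If the answer is then given to that person, or is visible to them, courtesy could raise it. Ratings of mixed objects cannot be separated after collection.

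**Working it through.** **1. The texts side by side**

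| Section | When | What is rated or discussed | Scored? |
|---|---|---|---|
| 9.1 | right after the exercise | exercise | yes |
| 9.7, weekly phone sessions | after the exercise and the call | exercise/session, exercise/phone session | yes |
| 9.7, program content | during the call | exercise | a review; no score mentioned |
| 1.2 | not stated | each exercise | criterion 7/10 |
| 10.1 | weekly, moment not stated | each exercise | threshold 7.0/10 |

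Section 9.7 assigns the first exercise as preparation for the first call, and each call reviews the week's exercise and assigns the next one. The exercise therefore precedes the call. A rating made right after the exercise is a pre-call rating, and a rating made after the exercise and the session is a post-call rating. There are two rating times and two objects. Sections 1.2 and 10.1 match the object in 9.1.

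**2. The plan's own figure for this score**

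Section 10.2 claims 95% power for acceptability with 30 participants, based on a prior mean utility of 7.8 and SD 1.8.

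- SE = 1.8/√30 = 0.329.
- Two-sided 0.05: Φ(0.8/0.329 − 1.96) = Φ(0.474) = 68%.
- One-sided 0.20: Φ(2.434 − 0.842) = 94%, but 10.2 does not state that level.
- If 1.8 is the SD of single ratings and nine are averaged per person, two-sided power is 97.7% at a within-person correlation of 0.3 and 90.4% at 0.5. The documents give no correlation.

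The 95% is thus not reproduced at two-sided 0.05 when 1.8 is taken as the between-person SD. That is a separate matter, and the present point does not rest on it.

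**3. How sensitive the cut would be to a shift (illustration only)**

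Inputs: SD 1.8 and n = 30 from section 10.2; cut 7.0 from section 10.1. The true means and the shifts are assumptions.

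P(observed mean ≥ 7.0) = 1 − Φ((7.0 − true mean − shift)/0.329)

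| True mean | No shift | +0.3 | +0.5 |
|---|---|---|---|
| 6.6 | 11% | 38% | 62% |
| 6.8 | 27% | 62% | 82% |

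For 6.8 with no shift: 1 − Φ(0.2/0.329) = 1 − Φ(0.609) = 27%. With +0.3: Φ(0.1/0.329) = Φ(0.304) = 62%. At the plan's expected mean of 7.8 with no shift: Φ(0.8/0.329) = Φ(2.434) = 99%.

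The SD of 1.8 belongs to utility alone in prior work, whereas 10.1 uses ease and utility combined, so 0.329 is only a stand-in for the real standard error. Were that error smaller, the 27% would fall and the 62% would rise.

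**The case against.** **Three rating times.** A reader might count the in-call review as a third. The documents do not support this. That paragraph lists what a call covers and mentions no score, so it can be read as a discussion of ratings already made.

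**The score is biased upward.** A reader might also infer this. Nothing in the documents shows it. No section says the score is given to the interventionist, and the general REDCap statement in 9.6 could cover these ratings. Their absence from Table 4 proves little, because that table lists only the three main assessments. What stands is that collector and route are unstated, so the bias cannot be ruled out.

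**Liking the call is part of liking PATH.** The endpoint in 8.0 is about the intervention, and 9.2 describes PATH as exercises plus calls. This is a fair argument for measuring the session too, and the choice of object belongs to the investigators. But 1.2 and 10.1 already apply the threshold to the exercise. If the session is meant to count, those two sections need changing.

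**The slash in 9.7 may mean two separate items.** If so, an exercise-only score exists, but its timing still conflicts with 9.1.

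**The illustration is selective.** This is correct. It uses true means just below the cut. At 7.8 an upward shift would change almost nothing, since the cut is already reached 99% of the time.

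**Conclusion.** The inconsistency holds. Sections 9.1 and 9.7 define different ratings for a component of the primary endpoint, and only the 9.1 version matches the object in 1.2 and 10.1. Scores taken under 9.7 would mix in the phone session and would follow a conversation with the interventionist about the same two qualities.

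An upward desirability bias is plausible under 9.7 and cannot be excluded. Its existence, direction and size are not established. The rise from 27% to 62% rests on an assumed true mean of 6.8, an assumed shift of +0.3, SD 1.8 and n = 30. It shows that a verdict near the cut would be sensitive to such a shift, not that the shift occurs.

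The point does not invalidate the design. It should be settled because the correction is cheap and the measure is primary.

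**What to change.** State one rating in the same words in 9.1, 9.7 and 10.1: ease and utility of the exercise only, entered by the patient through a REDCap link or on paper, after the exercise and before the call, and not shown to the interventionist.

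- Say that the in-call review of ease and utility is not scored.
- If a rating of the phone session is wanted, record it as a separate item outside the 7.0 rule.
- Leave the happiness and optimism ratings before and after each session as they are, since the GEE analysis in 10.1 needs them.
- While editing, align the response scale: 9.7 says "all using 10-point Likert scales", whereas the 10.1 anchors, "0=very difficult/not helpful; 10=very easy/very helpful", span eleven whole-number points.

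The cost is one short form per week for nine weeks in the PATH arm, and perhaps a few more missing ratings, which a reminder before the call would limit. Comparability with the prior studies that supplied the 7.0 threshold may weaken if they timed the rating differently; the documents do not say how they did.
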